3.4 Sample Size

The sample size for the quasi-experimental pre-post study is calculated separately for each country, based on comparison between pre- and post-intervention periods. The following assumptions are used:

- ξ power 80%
- ξ alpha level of 0.05
- ξ pre-intervention referral to a higher level of care 3%, with a minimum detectable difference of 50%
- ξ pre-intervention antibiotic prescription of 60%
- ξ intra-cluster correlation coefficient (ICC) of 0.005 for referral and 0.05 for antimicrobial prescription
- ξ Kenya – estimated average cluster size of 230 children / month (assuming a cluster ratio of health centres : dispensaries 1:2, with 100 / month in dispensaries and 500 / month in health centres)
- ξ Senegal – estimated cluster size of 170 children per month

For the referral primary outcome, we therefore initially estimated requiring the following sample size:

- ξ Kenya – 17 facilities, recruiting an average of 690 children per quarter per facility, equating to 11,730 children per quarter
- ξ Senegal – 18 facilities, recruiting an average of 510 children per quarter per facility, equating to 9,180 children per quarter

For the antibiotic prescription primary outcome, this would enable a minimum detectable reduction of 18% in Kenya and Senegal.

Following lower than anticipated recruitment in the pre-intervention period, sample size calculation was revised. As a result, two additional facilities were added per country and the pre-intervention period was extended from an initially anticipated 3 months to a 6 – 8 month period. A decision was also taken to target a post-intervention sample size of at least the same as the pre-intervention sample size, as well as a minimum duration of 9 months post-intervention to allow for stabilisation over time and some seasonal overlap of pre- and post-intervention periods.

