4 STATISTICAL PRINCIPLES

4.1 Confidence Intervals and p-Values

Results estimates of primary and secondary outcomes will be presented along with the associated two-sided 95% confidence intervals.

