4.2 Intervention adherence and Protocol Deviations

While in Kenya pulse oximeter was indicated for all children, in Senegal, pulse oximeter was indicated for all young infants and for older children with cough/difficult breathing or red/yellow IMCI classification. Cough/difficulty breathing and red/yellow IMCI classification are defined two ways, based on signs and symptoms as reported by the caregiver pre-consultation or on diagnosis made by the healthcare provider during the consultation. These definitions are detailed in a separate document and both will be used, separately, to assess intervention adherence.

Adherence will be evaluated on the basis of pulse oximeter and CDSA use when indicated.

- ξ Pulse oximetry adherence will be evaluated primarily using information on SpO2 values from clinical records. Pulse oximetry will be considered used if the RA has found any SpO2 recording (value readable or unreadable). Pulse oximetry will be considered not used if the RA did not find any recorded SpO2. Adherence will be additionally evaluated based on pulse oximetry use as reported by the caregivers.

- ξ CDSA adherence will be evaluated by comparing the number of children enrolled and the number of children recorded into the CDSA database. These data will be used to explore further and in more details adherence to the CDSA, but outside the scope of this SAP and it will be detailed in a separate document.

Adherence will be reported overall and weekly by facility.

The following information will be summarised by arm to evaluate deviations to the study protocol:

- ξ Number and percentage of caregivers for which no Day 7 follow-up was attempted.

More general deviations will be recorded by the study team in a study deviation log and categorised into minor and major.

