6.1.2 Health, hospitalisation and referral outcomes

6.1.2.1 Proportion of children with a severe complication by Day 7

Severe complication is defined as death or secondary hospitalisation. Secondary hospitalisation refers to any delayed hospitalisation (occurring at any point greater than 24hrs after the Day 0 consultation) and any hospitalisation occurring without a referral. Information on death and hospitalisation will be taken from Day7 follow-up assessment.

Death will be counted in the numerator if death date is within 7 days of Day0 (7th day included). Hospitalisation will be counted in the numerator if the child was not referred at Day0 or hospital admission date is within 7 days of Day0 (7th day included) but after 24hrs of Day0.

The denominator will be all children recruited. Children for whom no death and hospitalisation data are available or withdrew prematurely from the study will be assumed to be alive and not hospitalised by Day7.

6.1.2.2 Proportion of children admitted to hospital within 24 hours of Day 0 consultation and as a result of a referral

Information on hospitalisation will be taken from Day7 follow-up assessment.

Hospitalisation will be counted in the numerator only if the child received a referral advice (as per definition above) at Day0 and hospital admission date is within the end of the following day. The denominator will be all children recruited.

Additionally, the proportion will be calculated and reported using only children who were referred as denominator.

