6.1.2.5 Proportion of children who completed referral as reported at Day 7 follow-up

A referral will be considered completed if a child attended a hospital, whether he/she was admitted or not. Children will be counted in the numerator if they received a referral advice (as per definition above) and their caregiver reported to have sought care in a hospital and the follow-up date is within 7 days of Day 0, considering a + 3 days window (10th day included). The denominator will be all children recruited.

Additionally, the proportion will be calculated and reported using only children who were referred as denominator.

Children for whom no Day7 data are available or withdrew prematurely from the study will be assumed not attending a hospital by Day7.

6.1.2.6 Proportion of children with non-severe disease referred to a higher level of care on Day 0

Children with non-severe disease who received a referral advice (as per definition above) at Day0 will be counted in the numerator. The denominator will be all children recruited. Non-severe disease will be defined in a separate document.

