6.3 Missing Data

Missing values will be primarily due to children lost to follow-up and not reached at Day 7.

Primary outcomes are based on information collected at Day0 through a structured data collection process that prevents missing values due to compulsory data entry. Therefore, missing data on the primary outcomes are not anticipated.

Analysis on secondary outcomes that rely on Day 7 follow-up data will be performed assuming the best case scenario (alive and not hospitalised) for children lost to follow-up or withdrawn.

Additionally, missing data will be described by pre and post intervention period and by relevant indicators, such as referral and severe disease to visually inspect for imbalances.

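### Children without Day 7 data are counted as non-events on three hospital-based secondary outcomes with no sensitivity analysis, so a difference in loss between periods would move the ratios, and best case is the wrong label for two of them

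*SAP*

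**What the plan says.** SAP 6.3 expects missing values mainly from children not reached at Day 7. For the secondary outcomes that depend on that contact, analysis "will be performed assuming the best case scenario (alive and not hospitalised) for children lost to follow-up or withdrawn". The outcome definitions apply this as follows.

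- **Severe complication (SAP 6.1.2.1).** Children with no death or hospitalisation data are taken as alive and not hospitalised. The denominator is all recruited children.
- **Admission within 24 hours as a result of referral (SAP 6.1.2.2).** There is no missing-data sentence. Hospitalisation is taken from the Day 7 assessment, "Hospitalisation will be counted in the numerator only if the child received a referral advice (as per definition above) at Day0" and the admission date falls by the end of the next day. The denominator is all recruited children, so a child with no Day 7 report cannot be counted as an event.
- **Completed referral (SAP 6.1.2.5).** Children with no Day 7 data "will be assumed not attending a hospital by Day7". The follow-up date must also fall by day 10.

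The two referral outcomes are additionally reported among referred children, but unreached referred children stay in that denominator. SAP 6.1.1 drops Day 7 assessments made more than 30 days after Day 0. SAP 4.2 lists as a deviation measure "Number and percentage of caregivers for which no Day 7 follow-up was attempted"; these children are counted there but not removed from the outcomes.

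The sensitivity analyses in SAP 6.2.4 vary the visits included, the referral definition, the period definition and the hospitalisation cut-off. On missing data, SAP 6.3 adds a description by period and by indicators such as referral, for visual inspection.

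**The concern.** The two periods are sequential (6–8 months, then 9–12 months; protocol 5.2), so phone follow-up is done at different times. SAP 6.2.4 itself mentions a strike in Senegal and a phase of intensive supervision in Kenya. Equal loss in the two periods therefore cannot be presumed as it might be between concurrent randomised arms. When a missing child is a non-event, a change in the share of children reached looks like a change in the outcome, and the confidence intervals treat the assigned values as observed.

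The direction also differs by outcome. Protocol 6.4.1 says the aim is to raise referral of children with severe disease, and uses 24-hour admission as the proxy for appropriate referral. Not admitted and not attending are therefore the unfavourable values for those two outcomes. One unreached child is scored favourably on severe complication and unfavourably on both referral outcomes, under a single best-case heading. What is at stake is the reading of the only death and hospitalisation comparison and of the two measures of whether referral worked.

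**Working it through.** **1. Reproduce the plan's figure, to fix the number of children.** SAP 3.4 gives 80% power, "alpha level of 0.05", a 3% referral rate rising by a relative 50% to 4.5%, and an "intra-cluster correlation coefficient (ICC) of 0.005 for referral and 0.05 for antimicrobial prescription". SAP 4.1 specifies "associated two-sided 95% confidence intervals". The two-proportion formula without continuity correction gives 2,518 children per period before clustering. The design effect is 1 + (m − 1) × ICC.

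- Kenya: 1 + 689 × 0.005 = 4.445; 2,518 × 4.445 = 11,193; 11,193/690 = 16.2, so 17 facilities and 17 × 690 = 11,730.
- Senegal: 1 + 509 × 0.005 = 3.545; 2,518 × 3.545 = 8,926; 8,926/510 = 17.5, so 18 facilities and 18 × 510 = 9,180.

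Both match the initial sizes in protocol 6.6.1.

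**2. Formula.** Let p be the true proportion and L the fraction without usable Day 7 data. If loss is unrelated to outcome, the analysed proportion is p × (1 − L), hence

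analysed RR = true RR × (1 − L_post)/(1 − L_pre).

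Under the same condition, an analysis of observed children returns the true RR.

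**3. No true effect.** The documents give neither loss rates nor levels for these outcomes, so all of these are assumptions: severe complication 1%; completed referral 1.8% of all children (3% referred × 60% completing).

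| Outcome | Loss pre / post | Analysed pre / post | OR |
|---|---|---|---|
| Severe complication | 5% / 15% | 0.95% / 0.85% | 0.89 |
| Severe complication | 5% / 10% | 0.95% / 0.90% | 0.95 |
| Severe complication | 10% / 5% | 0.90% / 0.95% | 1.06 |
| Completed referral, all recruited | 5% / 15% | 1.71% / 1.53% | 0.89 |
| Completed referral, among referred | 5% / 15% | 57% / 51% | 0.79 |

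The 24-hour admission outcome behaves like the first three rows at a 1% level. In the last row the risk ratio is again 0.85/0.95 = 0.89; the odds ratio lies further from 1 because the outcome is common.

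**4. A real effect.** Protocol 6.6.1 expects that completed referrals may rise by only 20–30%. With 5%/15% loss the analysed RR is 1.20 × 0.85/0.95 = 1.07 to 1.30 × 0.85/0.95 = 1.16. With the losses reversed it is 1.20 × 0.95/0.85 = 1.34 to 1.30 × 0.95/0.85 = 1.45.

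**5. Equal loss.** The ratio is unchanged. The risk difference, which SAP 6.2.1 also reports, is multiplied by (1 − L).

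**6. How often this would mislead.** Chance of p < 0.05 with no true effect at 5%/15% loss, normal approximation, sizes from step 1:

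| | ICC 0.005 as a full design effect | No clustering |
|---|---|---|
| Severe complication 1% | 6.7% | 11–13% |
| Completed referral 1.8% | 8.1% | 16–19% |

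The ranges are Senegal to Kenya. The same facilities serve both periods, so the two columns are best read as a rough bracket.

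**The case against.** The strongest reply is that little depends on this. Both primary outcomes are recorded at Day 0. Protocol 6.4.1 made severe complication secondary because a pre-post comparison supports it weakly, Table 8 of the protocol calls the outcome assessment exploratory, and SAP 6.2.1 models secondary outcomes only if numbers allow. Step 6 shows a modest rise in false positives under the full design effect. All of this stands and limits the weight of the point.

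The plan would also show an imbalance. SAP 5.4 reports the number followed up by period, SAP 4.2 the number never called, and SAP 6.3 missingness by period and referral status. A reader could derive some crude reached-only proportions from these. They are not pre-specified adjusted estimates, so they reveal the problem without correcting the models.

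Protocol 7.2.4 extends the hospital-record search to children lost to follow-up, whereas protocol 6.5.1 and 7.1.1 limit it to children reported to have attended. Even under the wider rule, the SAP takes hospitalisation for these outcomes from the Day 7 assessment, so recovered records would not enter them.

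Three stronger readings are tempting but unsupported.

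- *The results are biased.* The documents give no loss rate and no sign that it differs between periods.
- *Every Day 7 proportion is the true one times the follow-up rate.* This needs loss unrelated to outcome, and it fails for cure, where SAP 6.1.2.7 counts unreached children as cured.
- *The SAP explicitly labels non-attendance a best case.* SAP 6.1.2.5 states its own rule without that label, and for SAP 6.1.2.2 the fixed value is inferred from SAP 6.3 and the denominator. The mislabelling comes from the general sentence in SAP 6.3.

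**Conclusion.** The point holds as a gap in the analysis plan for three secondary outcomes. A fixed non-event value is assigned to every child without Day 7 data, nothing planned varies it, and the label in SAP 6.3 is right for severe complication but wrong for 24-hour referral admission and completed referral. Confidence is high on the text and on the missing sensitivity analysis. It is not high on whether any bias exists or how large it is. The odds ratio of about 0.89 rests on an assumed 5% v 15% loss unrelated to outcome; 5% v 10% gives 0.95, and equal loss gives no shift in the ratio. Effective loss also differs by outcome, because a call between day 11 and day 30 is usable for severe complication and 24-hour admission but scores as a failure for completed referral.

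**What to change.** In SAP 6.3 and 6.2.4, for severe complication, 24-hour referral admission and completed referral:

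- **(a)** Report, next to the all-recruited result, the same adjusted model restricted to children with an observed outcome. Define observed as a Day 7 assessment retained under the 30-day rule for severe complication and 24-hour admission, and as a call by day 10 for completed referral. State that this model assumes loss is unrelated to outcome given the covariates.
- **(b)** For the two referral outcomes, also report the proportion among referred children with observed Day 7 data.
- **(c)** Add opposite-assumption bounds, applied by period. Count unreached referred children as having attended and been admitted within 24 hours. For severe complication, give a worst-case or tipping-point range for unreached children. A full worst case will say little for a rare event: at 1% with 5% and 15% loss it gives 0.95% + 5% = 5.95% and 0.85% + 15% = 15.85%. The tipping-point form is therefore the more useful.
- **(d)** Remove the best-case label for the two referral outcomes.

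Do not make agreement in direction a condition for drawing conclusions. A 20–30% rise that reads as 7–16% keeps its direction and would pass such a test although much of the effect is lost. Show the estimates side by side.

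The cost is SAP wording, a few model runs on data already collected, more rows in the secondary table and slightly wider intervals in (a).

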6.4 Additional analyses

Primary outcomes will be further presented by adherence and indication groups (e.g. children for which pulse oximetry was indicated and was used, children for which pulse oximetry was indicated but was not used, etc.).

6.5 Harms

Safety of the interventions will be evaluated in terms of deaths and secondary hospitalisations that occurred throughout the course of the study. Deaths, secondary hospitalisations and both combined will be reported as counts and percentages. Summary statistics will be presented separately for each intervention as outlined in Section 4.3.

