4.3 Analysis Populations

All analyses will follow the intention to treat (ITT) principle, irrespective of any protocol violations.

No safety set will be defined but safety information will be reported overall and by use of intervention as defined in section 4.2.

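### The harms section splits deaths and secondary hospitalisations by use of the intervention but not by period, so neither event alone has a specified pre/post summary

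*SAP*

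**What the plan says.** SAP 6.5 sets the events: "Deaths, secondary hospitalisations and both combined will be reported as counts and percentages". It covers the whole study and defines the split by cross-reference: "Summary statistics will be presented separately for each intervention as outlined in Section 4.3". SAP 4.3 then states: "No safety set will be defined but safety information will be reported overall and by use of intervention as defined in section 4.2".

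SAP 4.2 defines use. Oximetry counts as used if the research assistant found any SpO2 entry, legible or not, and as not used otherwise. CDSA adherence is a comparison of children enrolled with children in the CDSA database. The section also says "Adherence will be evaluated on the basis of pulse oximeter and CDSA use when indicated", and on indication "While in Kenya pulse oximeter was indicated for all children, in Senegal, pulse oximeter was indicated for all young infants and for older children with" cough or difficult breathing, or a red or yellow IMCI classification.

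Outside the harms section:

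- Severe complication by Day 7 (death or secondary hospitalisation) is a secondary outcome (Protocol 6.4.1, SAP 6.1.2.1).
- SAP 6.2.1 summarises outcomes for each period and models secondary outcomes in the same way as the primary ones if numbers allow. Protocol 7.3.1 also plans a pre/post comparison.
- SAP 6.4 presents the primary outcomes by groups that combine indication and use.

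**The concern.** A safety summary should let a reader see whether deaths or unplanned admissions changed when the intervention arrived. The harms section does not use the contrast the study was built for. It uses one formed by what providers did during the consultation.

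Three things follow. First, deaths by period are visible only inside a composite whose other component depends on referral, which the intervention is meant to change. Second, where the device is directed at children more likely to be severely ill, users can show more events than non-users although the intervention does no harm. Third, the by-use groups are not fully defined: pre-period children have no stated place in them, and *each intervention* has no clear referent because SAP 3.1.3 describes one package, oximetry embedded in a CDSA.

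**Working it through.** **1. Figures to reproduce.** The documents give no death rate, complication rate or safety power, so there is no harms figure to recompute.

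**2. What is specified, event by event.**

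| Event | Harms section (SAP 6.5, 4.3) | By period elsewhere |
|---|---|---|
| Death alone | Overall; by use | Not specified |
| Secondary hospitalisation alone | Overall; by use | Not specified |
| Either | Overall; by use | Described for each period; modelled if numbers allow (SAP 6.1.2.1, 6.2.1) |

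As written, the overall line in SAP 4.3 is not divided by period.

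**3. Why the composite does not stand in for deaths.** Under SAP 6.1.2.1 an admission counts as secondary if the child was not referred at Day 0, or if it came more than 24 hours after the consultation. A referred admission within 24 hours does not count. Protocol 6.4.1 says the intervention aims to raise referral of children with severe disease. Let D be deaths and S surviving children with a secondary hospitalisation, so the composite count is C = D + S. If k surviving children move from delayed or unreferred admission to prompt, referred admission, and deaths change by d, then C changes by d − k. Whenever k exceeds d, C falls, even if d is positive.

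**4. The by-use contrast with no true effect.** Inputs:

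- s, the share of children in a higher-risk indicated stratum: 0.40 and 0.70. Protocol 6.3 puts cough or difficulty breathing at around 40 to 70% of primary care attenders; using this as the stratum size is an assumption.
- r1 and r0, event risk in that stratum and in the rest: 2% v 0.5%, and 2% v 1% (assumed).
- u1 and u0, device use in the two strata: 0.6 v 0.4, 0.8 v 0.2, 0.9 v 0.1 (assumed).

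Formulas:

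- Share using: p = s·u1 + (1 − s)·u0
- Risk in users: Ru = [s·u1·r1 + (1 − s)·u0·r0] / p
- Risk in post-period non-users: Rn = [s(1 − u1)r1 + (1 − s)(1 − u0)r0] / (1 − p)
- Risk in non-users if an equal-sized pre period is added to them: Rn′ = [r + (1 − p)Rn] / (2 − p), with r = s·r1 + (1 − s)·r0

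Largest case (s = 0.40, 2% v 0.5%, use 0.9 v 0.1):

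- p = 0.36 + 0.06 = 0.42
- Ru = (0.0072 + 0.0003)/0.42 = 0.0179
- Rn = (0.0008 + 0.0027)/0.58 = 0.0060; ratio 2.96
- With the pre period added: r = 0.011, Rn′ = (0.011 + 0.0035)/1.58 = 0.0092; ratio 1.95

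Smallest case (s = 0.70, 2% v 1%, use 0.6 v 0.4):

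- p = 0.42 + 0.12 = 0.54
- Ru = 0.0096/0.54 = 0.0178
- Rn = 0.0074/0.46 = 0.0161; ratio 1.11
- With the pre period added: Rn′ = (0.017 + 0.0074)/1.46 = 0.0167; ratio 1.06

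All cases, used v not used in the post period, with the pre-period-added ratio in brackets:

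| s | r1 v r0 | Use 0.6 v 0.4 | Use 0.8 v 0.2 | Use 0.9 v 0.1 |
|---|---|---|---|---|
| 0.40 | 2% v 0.5% | 1.30 (1.19) | 2.23 (1.65) | 2.96 (1.95) |
| 0.40 | 2% v 1% | 1.15 (1.10) | 1.51 (1.32) | 1.74 (1.45) |
| 0.70 | 2% v 0.5% | 1.18 (1.11) | 1.76 (1.31) | 2.39 (1.42) |
| 0.70 | 2% v 1% | 1.11 (1.06) | 1.39 (1.18) | 1.62 (1.24) |

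With the same case mix in both periods, the pre/post ratio is 1.00 throughout.

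**5. Where this mechanism applies.** Protocol 6.3 says the criteria followed in Senegal were chosen to find children most likely to be hypoxaemic and notes the raised risk in young infants; Protocol 3.1 ties hypoxaemia to mortality. In Kenya all children were indicated. Setting s = 1 gives Ru = Rn = r1, a ratio of 1.00, unless providers use or record the device selectively. The same holds in Senegal if the table is restricted to indicated children and use among them is unrelated to risk.

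**6. Pre-period children.** Facilities already using oximetry routinely were excluded (Protocol 6.2.1, SAP 5.2), so pre-period children could hardly be users. SAP 4.2 and 4.3 do not say whether they count as not used or are left out. The bracketed figures show that the choice changes the result.

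**The case against.** The strongest reply is that death is already compared before and after. It is a component of severe complication, the description by period is unconditional, and a model follows if numbers allow. This stands. A reader might infer that the plan never compares deaths across periods; the documents do not support that. Admission within 24 hours after referral is also a secondary outcome, and SAP 6.2.4 varies the cut-off between primary and secondary hospitalisation, so a shift in admissions would be partly visible. None of this shows deaths on their own.

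A second reply is that SAP 4.3 points to 4.2, which speaks of use when indicated, so the split may be meant only among indicated children. That is a fair reading and would remove most of the Senegal problem. But the rule for counting oximetry as used does not mention indication, and SAP 6.4 sets out indication groups for the primary outcomes only. Similarly, *each intervention* may mean oximetry and the CDSA taken separately, but the SAP does not say so.

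Third, a period split is confounded too. Protocol 6.4.1 keeps severe complications out of the primary outcomes because other events between the phases could affect them. This also stands. It calls for a caution beside the table, not for leaving the table out.

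Two further inferences are tempting. One is that users would show the full risk ratio between strata, 2%/0.5% = 4. That needs every indicated child measured, no other child measured, and no pre-period children among non-users, none of which the documents say. Adding an equal-sized pre period brings the 4 down to 0.02/[(0.011 + 0.003)/1.6] = 2.3 at s = 0.40, and to 0.02/[(0.0155 + 0.0015)/1.3] = 1.5 at s = 0.70. The other is that all pre-period children are placed in the not-used group; the plan is silent on this.

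**Conclusion.** The point holds as a gap in the specification and a weak choice of contrast. The harms section names no period, and deaths alone and secondary hospitalisations alone are not specified pre v post anywhere. The composite that is described by period can move through reclassification of admissions.

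The by-use contrast is confounded by indication in Senegal, and hence in pooled tables, unless it is limited to indicated children. In Kenya the indication rule creates no such bias. With no true effect, the apparent used v not-used risk ratio is 1.11 to 2.96 within the post period, or 1.06 to 1.95 if an equal number of pre-period children are counted as not used. These ranges rest on assumed risks, use rates and stratum sizes. They show direction and plausible scale and do not forecast this study's results. The analyses of the two primary outcomes are unaffected.

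**What to change.** In SAP 6.5 and 4.3:

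- Report deaths, secondary hospitalisations and both combined by period (pre, post), by country and pooled. Note beside the table that a pre/post difference may reflect other changes over time.
- If the by-use table is kept, restrict it to the post period, split it by indication as SAP 6.4 does for the primary outcomes, and label it descriptive. SAP 4.2 defines cough or difficulty breathing and the IMCI classification in two ways (caregiver report before the consultation, provider diagnosis), so say which is used for the indication split.
- Replace *each intervention* with the groups actually meant.

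The SAP already reports analyses overall and by country (section 6), and the study already collects the data. The cost is SAP wording and one table.
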